# **The Effect of White Light on Fatigue Levels in Patients With Gynecological Cancer: A Double Blind Randomized Trial**

**02.08.2021**

## **STUDY PROTOCOL**

### **Study design and participants**

[figure not shown]
This was a triple-blind randomized study. The study included two parallel groups consisted of 72 patients who met the inclusion criteria and were receiving outpatient chemotherapy for gynecological cancer. The sample size in this study was 72 subjects: 36 in the intervention group and 36 in the control group. This study was based on an effect size of 0.25, a first type error of 5%, and 80% power, relying on the results of a previous study that evaluated the effect of bright white light on the fatigue levels of patients with cancer.[16] Patients aged over 18 years, had a normal state of consciousness, had no communication disorders, did not work in the night shift, had a general fatigue level score of  $\geq 1$  according to the Brief Fatigue Inventory(1,2), and could perceive light were included in the study. Patients who had natural/artificial lenses, used medication that causes photosensitivity (tetracycline, doxycycline, nalidixic acid, voriconazole, amiodarone, hydrochlorothiazide, naproxen, piroxicam, chlorpromazine), and had a change in their treatment plan in the last 6 weeks were not included in the study.

A total of 132 women were admitted to the clinic at the time of the study. All of them were evaluated as per the conditions of inclusion criteria. Twenty-five women who did not meet the inclusion criteria and another 12 who refused to participate in the study were not included in the study. Therefore, a total of 89 women, 47 in the intervention group and 42 in the control group, were included in the study through randomization. However, six women from the intervention group and three from the control group were excluded from the study because of various reasons such as rejecting white light administration, familial reasons, and reaching saturation in stratification according to the fatigue level factor. Thus, the study was conducted

with a total of 72 women with 36 in each group (Figure). Patients and at least one of their relatives were informed about the research process and the use of white light in the patient room, along with visual materials. It was ensured that the informed consent form was ready by the patient and, if necessary, a relative. After obtaining written consent and signatures from the patients, the study was initiated.

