### **Randomization and blinding**

The study participants were stratified into intervention and control groups using stratified and block randomization methods, respectively. Firstly, patients who met the inclusion criteria and accepted to participate in the study were stratified according to the severity of fatigue (1-3 points, mild; 4-6 points, moderate; 7-10 points, severe fatigue). For block randomization, at least 10 blocks were selected by random drawing among 20 blocks (permutations block 6 and block of size 3 with 1:1) produced by the researchers on SAS 9.4 (SAS Institute Inc., Cary, NC) software package (3-5). Random assignment was continued until there were an equal number of patients (12 patients in each 3 strata) according to their fatigue levels in each group, and the groups consisted of 36 patients (Figure).

**Figure.** Diagram of participant flow through study

A researcher among the authors who was not involved in patient care and implementation of interventions evaluated patients for eligibility, enumerated them, collected baseline data, and assigned them to research groups. Moreover, this researcher assigned the research groups at the beginning of the research, the intervention group “A,” whereas the control group was coded with the letters “B.” Two research assistants (RA) were recruited and trained for this study. Research assistants were two nurses with a bachelor’s degree, who were independent of each other and the researchers. The groups to which the patients belonged were reported to the nurses using the appropriate letter code. The first nurse (RA1) who made the interventions to the intervention group. The post-intervention evaluation of the patients in the application and control groups and the entry of the obtained data into the statistics program were made by the other nurse (RA2) who was not informed about the application. Thus, the nurse (RA2) who conducted the evaluations, were blinded. During data entry, coding of the groups was continued. A biostatistician, who was unaware of the purpose of the research, interventions, and groups, performed statistical analysis on the research data. Further, the coding of the groups was terminated by the authors at the end of the analysis. In this manner, double blinding was achieved in the study.

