### **Outcomes and instruments**

Observation, interview, and measurement methods were used to collect the data. “Brief Fatigue Inventory (BFI)” and “Descriptive Information Form” were used to evaluate the fatigue level of the patients on the first, ninth, and twenty-first days. The patients’ demographic and medical characteristics were obtained from their medical records.

*The Descriptive Information Form:* This form was used to collect information on the sociodemographic characteristics, diseases, and treatments of the patients.

*The Brief Fatigue Inventory (BFI):* This inventory was developed by Mendoza et al. (1999) to evaluate the general fatigue level and its effect on activities of daily living in patients with

cancer. The study evaluating its validity and reliability for the Turkish context was carried out by Çınar et al.(2000) Cronbach's alpha internal consistency coefficient of the inventory was found as 0.98. The BFI consists of nine items in total, with three evaluating general fatigue and six evaluating the effect of fatigue on daily life. Individuals rate all items on a scale of "0" (no fatigue) to "10" (the most severe fatigue you can experience), taking into account their status in the last 24 hours. The "general fatigue" level is calculated by taking the average of the first three items of the inventory. The average of the last six items yields a score for the effect of fatigue on the activities of daily living. According to the scores obtained from the BFI, the severity of fatigue of the individual was "0, no fatigue; 1-3, mild; 4-6, moderate; and 7-10, severe fatigue".

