### **Interventions**

Descriptive Information Form and the BFI were administered to the patients in both groups on the first day of the application phase, and their baseline assessment was made, which was followed by interventions for energy conservation (organizing the patient's sleep-rest hours, supporting activities of daily living, organizing the living environment, etc.) and energy enhancement (adequate and balanced nutrition). The patients were informed about the study procedure. Between the second and the eighth days of the application phase, the patients in the intervention group were administered a standard white light at 10,000 Lux intensity by an independent nurse (RA1) in their home environment using a Litebook Elite light source (The Litebook Company Ltd., Medicine Hat, AB). The distance between the light source and the patient's face was set at 50 cm, and the intensity of the light for each patient was checked using a Lux Meter. The intervention was applied between 07:00 and 10:00 in the morning for 30 minutes without interruption, and it was continued for seven successive days. The light application procedure was followed based on the previous studies on oncology patients. [16,25] The patient was asked to engage in other activities during the light administration, such as

watching television, reading books, and not to look directly at the light. The second and third evaluations of the fatigue status of both groups of patients were completed on the 9th and 21st days by an independent other nurse (RA2).

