### **Data analysis**

The statistical analysis was performed on IBM SPSS v.24 (SPSS, Chicago, IL) software package. To compare the socio-demographic characteristics of groups, independent groups t-test and chi-square analysis were used. Paired samples t-test was used to determine differences between the study groups, and analysis of variance (repeated measurements ANOVA) was employed in repeated measurements. To ensure the balance between the groups and the reliability of the intervention results, the intention-to-treat method was not used in the analyses. Statistical significance level was accepted as  $p < 0.05$ .

2. Çınar S, Sezerli M, Sarsmaz N, Menteş AÖ. Hemodiyaliz akut yorgunluk sendromuna neden olabilir mi. *Hemşirelik Forumu Derg*. 2000;3:28–33.
3. Broglio K. Randomization in clinical trials: permuted blocks and stratification. *Jama*. 2018;319(21):2223–4.

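### The planned repeated-measures ANOVA ignores the day-1 stratification and appears to use untreated day 1 as an outcome, so it is conservative and can lose much power that an ANCOVA on the same 72 women would keep

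*Combined protocol and SAP*

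**What the plan says.** - Study design and participants: "The sample size in this study was 72 subjects: 36 in the intervention group and 36 in the control group". The basis is "This study was based on an effect size of 0.25, a first type error of 5%, and 80% power". The section does not give the metric of 0.25, the tested term, the sidedness or any between-day correlation.
- Randomization and blinding: women are "stratified according to the severity of fatigue (1-3 points, mild; 4-6 points, moderate; 7-10 points, severe fatigue"), and for both arms "Random assignment was continued until there were an equal number of patients (12 patients in each 3 strata) according to their fatigue levels".
- Outcomes and instruments: the BFI and the descriptive form "were used to evaluate the fatigue level of the patients on the first, ninth, and twenty-first days". General fatigue is the average of the first three BFI items.
- Interventions: day 1 is the baseline assessment, and light comes after it: "Between the second and the eighth days of the application phase, the patients in the intervention group were administered a standard white light".
- Data analysis: "Paired samples t-test was used to determine differences between the study groups, and analysis of variance (repeated measurements ANOVA) was employed in repeated measurements". The level is p < 0.05. No stratum term, day-1 covariate or deciding term is named.

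**The concern.** The randomisation makes the arms equal on severity stratum, and the stratum is a coarse version of day-1 fatigue. Two things follow if an ANOVA takes days 1, 9 and 21 as its three measures.

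(a) Day 1 precedes any light and carries no treatment effect. The group term averages it in, so the effect is diluted to two thirds. The group-by-time term contrasts the later days with day 1 and carries its noise.

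(b) The part of day-1 fatigue explained by stratum cannot differ between arms. A model without stratum or day 1 still leaves that part in its error term, so the standard error is too large for this design and the test rejects less often than its nominal 5%.

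The risk is a missed benefit, not a false positive. A null result could come from the model rather than from the light. Because neither ANOVA term is named as deciding, the two may also give different answers on the same data.

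**Working it through.** **Inputs from the documents.** 36 per arm; 12 per stratum per arm; strata 1-3, 4-6 and 7-10; three assessments (days 1, 9, 21); light on days 2 to 8; 5% level.

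**Assumptions.** Equal SD (set to 1) on the three days; equal correlation ρ = 0.3, 0.5 or 0.7; day-1 scores uniform within each stratum; two-sided test; 0.25 read as Cohen's f. For two arms at one assessment, f = 0.25 means a difference of 0.5 SD. That is this review's benchmark, not the plan's.

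**1. The plan's own figure.** The stated inputs do not fix N.
- One assessment, f = 0.25: 126 to 128 women in total.
- Group term of a three-measure ANOVA: λ = f²·N·m/(1+(m−1)ρ) = 0.0625×72×3/(1+2ρ) = 13.5/(1+2ρ). N = 72 is the smallest adequate total at ρ = 0.32 to 0.33 (λ = 8.23 to 8.13, power 0.808 to 0.803). At ρ = 0.5 the total would be 86.
- Group-by-time under sphericity: λ = 13.5/(1−ρ), with power at least 0.91 at 72.

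With no effect on day 1, the group term has f = (d9+d21)/6. So f = 0.25 requires d9+d21 = 1.5 SD, an average of 0.75 SD on the two treated assessments.

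**2. Variance held by the strata.** Stratum means are 2, 5 and 8.5, with overall mean 5.167. Between-stratum variance is (3.167²+0.167²+3.333²)/3 = 7.056. Mean within-stratum variance is (4/12+4/12+9/12)/3 = 0.472. The share is R² = 7.056/7.528 = 0.937.

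**3. Type I error of the group term.** A woman's three-day mean has variance v = (1+2ρ)/3. The balanced part is v²R², so the true variance of the arm difference is k = 1−vR² times what the model uses. The actual two-sided level is about 2Φ(−1.994/√k).
- ρ = 0.3: v = 0.533, k = 0.500, 1.994/√k = 2.82, level 0.5%.
- ρ = 0.5: v = 0.667, k = 0.375, 3.26, level 0.1%.
- ρ = 0.7: v = 0.800, k = 0.250, 3.99, level below 0.1%.

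**4. Power of the group term for 0.5 SD on days 9 and 21.** The difference in three-day means is (0+0.5+0.5)/3 = 0.333. At ρ = 0.3 the rejection limit is 1.994×√(0.533×2/36) = 0.343 and the true standard error is √(0.500×0.533×2/36) = 0.122. Power is Φ((0.333−0.343)/0.122) = 0.47.

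**5. Day-1-adjusted mean of days 9 and 21.** The residual variance is (1+ρ)/2−ρ² = 0.56, 0.50 and 0.36. Standard error √(variance×2/36) = 0.176, 0.167 and 0.141. So 0.5/SE = 2.83, 3.00 and 3.54, and power is 80%, 84% and 94%.

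**6. Simulation of the same design**, analysed by the unadjusted ANOVA and by the adjusted mean (ρ = 0.3 / 0.5 / 0.7):

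| | Group | Group-by-time | Adjusted mean |
|---|---|---|---|
| Type I error, % | 0.5 / 0.1-0.2 / <0.1 | 2.5 / 3.0 / 3.5-3.8 | 4.9 / 4.9 / 5.0 |
| Power, 0.5 SD both days, % | 46 / 33 / 20 | 40 / 58 / 83 | 80 / 84 / 94 |
| Same, arms not stratified, % | 48 / 40 / 34 | 43 / 57 / 81 | not shown |
| Power, 0.75 SD both days, % | 89 / 83 / 75 | 85 / 95 / 99 | not shown |

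Without stratification, the type I error of both ANOVA terms returns to about 5%.

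**7. Sensitivity of the type I error.**
- R² = 0.89 (adjoining bands 1-4, 4-7, 7-10, uniform): group 0.8 / 0.2 / <0.1%; group-by-time 2.7 / 2.9 / 3.7%.
- R² = 0.5: group 2.2 / 1.7 / 1.1%; group-by-time 3.2 / 3.7 / 4.3%.
- Later SD 0.7 of the day-1 SD: group-by-time 0.7 to 0.8%.

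The direction is the same throughout; the size is not.

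**The case against.** The strongest reply is that the model is partly inferred. The Data analysis section does not say that day 1 enters the ANOVA or that the ANOVA has a between-arm factor. It attaches group differences to a paired t-test, which has no natural pairs between independent arms. This stands as a limit. Three dated assessments and a repeated-measures ANOVA make the reading natural, but not certain. The other reading is no better: if the ANOVA was run only within each arm, the misapplied paired test is the only between-arm comparison left.

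Four stronger inferences are tempting, and the documents do not support them.
- *That the 5% level is exceeded.* The departure is downward, so 5% remains an upper bound.
- *That 72 is too few, or that the stated 80% is wrong.* With no metric, term or correlation given, 80% cannot be checked. For 0.75 SD on both days, group-by-time exceeds 80% at all three correlations and the group term does so at two of them. The low figures belong to the 0.5 SD benchmark.
- *That stratification causes the power loss and the disagreement between the two terms.* At ρ = 0.3 the group term has only 48% even without stratification, so the untreated day 1 is the main cause. Stratification adds noticeably only at higher correlations (34% falls to 20% at ρ = 0.7). The two terms disagree in 22/29/63% of trials with stratification, against 49/52/60% without it, so at 0.3 and 0.5 the design reduces disagreement.
- *That the printed limits guarantee a large stratum share.* General fatigue averages three items, so values such as 3.33 and 6.67 can occur between the printed bands. No firm lower bound follows.

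It is also fair to say that choosing a better-powered model after the data are in is post hoc. The fix has to respect that.

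**Conclusion.** The point holds as a mismatch between design and analysis, provided day 1 is one of the repeated measures. The ANOVA as written is conservative. Under equal SDs and uniform scores within strata, its group term works at about 0.5% or less and group-by-time at about 2.5 to 3.8%. For 0.5 SD on days 9 and 21, it gives 20 to 46% power (group) or 40 to 83% (group-by-time), where adjustment for day 1 gives 80 to 94%. The untreated day explains most of the group term's loss; the unmodelled strata explain the low type I error.

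The correlations, the SDs, the stratum share and the reading of 0.25 are assumptions, because the documents give none of them. The direction of the type I departure held in every setting tried, but the exact percentages are not properties of this plan. The missing basis for 72 is a gap in reporting, not proof of an error in the number. The reason to act is the available adjustment, which brings the test back to about 5% and raises power for an effect on both later assessments.

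**What to change.** Replace the unadjusted ANOVA, and the paired t-test attached to group differences, with one deciding between-arm test. For example: *BFI general fatigue on days 9 and 21 (mean of the two) is compared between arms by ANCOVA, adjusted for day-1 BFI general fatigue and fatigue stratum, two-sided 5%. With 36 per arm, power for a 0.5 SD difference on both days is about 79/84/93% at assumed correlations 0.3/0.5/0.7.* One named day may be used instead of the mean. Alongside it, state the metric of 0.25 and the test and correlation behind 72. If the ANOVA is kept unchanged, name group-by-time as the deciding term and report its 40/58/83% for that difference.

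**Cost.** Wording and one re-run on data the trial already collects; no extra patients.

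**Downside.** If light acts on one of the two days only, the two-day mean has about 29/32/42% power for 0.5 SD on that day, against 39/55/81% for group-by-time. Adjusted day 9 alone has 59/68/83% if the effect is on day 9. The day or days must therefore be fixed before the comparison is seen. If the data have already been analysed, report the ANCOVA as a labelled post hoc analysis beside the original.

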### **Randomization and blinding**

The study participants were stratified into intervention and control groups using stratified and block randomization methods, respectively. Firstly, patients who met the inclusion criteria and accepted to participate in the study were stratified according to the severity of fatigue (1-3 points, mild; 4-6 points, moderate; 7-10 points, severe fatigue). For block randomization, at least 10 blocks were selected by random drawing among 20 blocks (permutations block 6 and block of size 3 with 1:1) produced by the researchers on SAS 9.4 (SAS Institute Inc., Cary, NC) software package (3-5). Random assignment was continued until there were an equal number of patients (12 patients in each 3 strata) according to their fatigue levels in each group, and the groups consisted of 36 patients (Figure).

**Figure.** Diagram of participant flow through study

A researcher among the authors who was not involved in patient care and implementation of interventions evaluated patients for eligibility, enumerated them, collected baseline data, and assigned them to research groups. Moreover, this researcher assigned the research groups at the beginning of the research, the intervention group “A,” whereas the control group was coded with the letters “B.” Two research assistants (RA) were recruited and trained for this study. Research assistants were two nurses with a bachelor’s degree, who were independent of each other and the researchers. The groups to which the patients belonged were reported to the nurses using the appropriate letter code. The first nurse (RA1) who made the interventions to the intervention group. The post-intervention evaluation of the patients in the application and control groups and the entry of the obtained data into the statistics program were made by the other nurse (RA2) who was not informed about the application. Thus, the nurse (RA2) who conducted the evaluations, were blinded. During data entry, coding of the groups was continued. A biostatistician, who was unaware of the purpose of the research, interventions, and groups, performed statistical analysis on the research data. Further, the coding of the groups was terminated by the authors at the end of the analysis. In this manner, double blinding was achieved in the study.

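### No allocation concealment is described, and the author who screens women and collects baseline data also assigns the groups and knows which code is the light arm

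*Combined protocol and SAP*

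**What the plan says.** All references are to the combined protocol and SAP.

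- **Roles.** Randomization and blinding introduces "A researcher among the authors who was not involved in patient care and implementation of interventions". This one person "evaluated patients for eligibility, enumerated them, collected baseline data, and assigned them to research groups". The text adds that "this researcher assigned the research groups at the beginning of the research", with A for intervention and B for control.
- **Sequence.** The same section says the blocks were "produced by the researchers on SAS 9.4". Blocks were drawn from a set of 20, with 1:1 allocation, until each of three fatigue strata held 12 women per arm.
- **Order of steps.** In that section, "patients who met the inclusion criteria and accepted to participate in the study were stratified according to the severity of fatigue", and block randomization follows.
- **Fatigue score.** Under Study design and participants, eligible women "had a general fatigue level score of" 1 or more on the Brief Fatigue Inventory (BFI). Under Outcomes and instruments, the general fatigue "level is calculated by taking the average of the first three items of the inventory". So the same measure governs entry and stratum.
- **Safeguards stated.** The assigning author takes no part in care or in giving the light. A second nurse, not told about the intervention, does the follow-up assessments. The biostatistician is unaware of the groups.

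The document does not say who held the list, how each allocation was released, or whether the assigning author could see the next one.

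**The concern.** Concealment keeps whoever decides on a woman's entry from knowing which arm she would join. Here the plan gives both tasks to one person, who also knows what the letters mean. The stated safeguards protect delivery, follow-up assessment and analysis. None of them acts at the moment of enrolment.

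The exposure matters more than usual in this trial. The outcome is self-rated, patients can see the lamp, and no sham light is described for controls. Blinding of patients therefore offers little protection, and unpredictable allocation has to carry more of the weight. A screener who can anticipate the next assignment could change the order or timing of enrolment, so that the arms differ in prognosis before treatment starts.

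**Working it through.** **1. The plan's own figure.** The block description mentions both 6 and 3. A block of 3 cannot be split 1:1, so I read it as blocks of 6 with 3 per arm. The number of such blocks is C(6,3) = 20, which reproduces the plan's 20.

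**2. Allocations known with certainty.** These are the places left once one arm of a block is full. Their expected number is the sum of the chances that the last 1, 2 and 3 places are all the same arm:

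1 + 2 × C(4,1)/20 + 2 × C(3,0)/20 = 1 + 0.4 + 0.1 = 1.5 of 6, or 25%. Over 72 women that is 18.

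**3. Best guess.** The guesser names the arm with more places left and tosses a coin when they are equal. The arms are equal at the start (probability 1), after two allocations (2 × 6/20 = 0.6) and after four (0.6), so ties number 2.2 per block. Correct guesses are 3 + 2.2/2 = 4.1 of 6, or 68.3%. Over 72 women that is about 49, against 36 with no foreknowledge. Sight of the list would give 100%.

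**4. Are the conditions for step 3 met?** It needs past assignments within the stratum and the block size. Someone who makes the assignments and sets the letters would ordinarily know the first. The second is plausible, because the researchers made the blocks, but it is not stated for this person.

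**5. Illustration of bias.** Let Δ be the assumed difference in prognosis between women enrolled when light is expected and when control is expected, with steering at every allocation. The bias is (2g − 1) × Δ, where g is the proportion guessed correctly. With g = 0.683 the factor is 0.367; with an open list it is 1.

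| Assumed Δ (BFI points) | Bias by guessing | Bias with open list |
|---|---|---|
| 0.25 | 0.09 | 0.25 |
| 0.5 | 0.18 | 0.5 |
| 1 | 0.37 | 1 |

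On a standardised scale, take 36 per arm and a two-sided 5% test. The standard error is √(2/36) = 0.236 SD, and the false-positive rate is Φ(bias/0.236 − 1.96) + Φ(−bias/0.236 − 1.96). For Δ from 0.10 to 0.50 SD, the bias by guessing is 0.037 to 0.183 SD and the false-positive rate is 5.3% to 12.2%. With an open list it is 7.1% to 56.4%. The documents give no value for Δ, so these figures show sensitivity only.

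**6. Room for discretion.** A mean of three whole-number items moves in thirds. Scores of 3.33, 3.67, 6.33 and 6.67 fall between the printed strata (1-3, 4-6, 7-10), and no rounding rule is given.

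**The case against.** The strongest reply is that the text is silent on the release mechanism. To say that someone assigned patients fits opening a sealed envelope as well as reading an open list. The researchers who made the blocks are not identified as this person. This stands: a reader might infer that allocation was unconcealed and enrolment was steered, and the documents show neither. It does not answer the point about roles, because an author who opens envelopes still learns past assignments and can use step 3 if the block size is known.

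Other replies have partial force:

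- **Acceptance came before stratification and assignment.** This limits what can be done after a woman agrees. It does not control whom the screener approaches, or when.
- **All 132 women were evaluated.** With 25 ineligible and 12 refusing, 132 − 25 − 12 = 95 remain and 89 were randomised. Selective exclusion therefore had limited room, although six women are unexplained and reordering remains possible.
- **The BFI is self-rated.** The screener cannot easily choose a woman's score. Discretion is confined to placing scores that fall between strata. That the day-1 baseline score is the one that set the stratum is also an inference.
- **Measured imbalance can be adjusted for.** This is correct for baseline BFI. It does not reach unmeasured differences in prognosis.

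The 47 v 42 split might be taken as a sign of steering. It is not: three strata with an unfinished block of 6 in each can differ by up to 3 × 3 = 9 without any interference.

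**Conclusion.** The point holds as a weakness in the stated role structure. One author who knows the code judges eligibility, collects baseline data and assigns groups, and no concealment is described. The stated safeguards do not cover foreknowledge at enrolment.

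The supportable size is the predictability: 68.3% guessable and 25% certain, if past assignments and a fixed block size of 6 are known. No bias in BFI points can be claimed, because each such figure depends on an assumed prognostic gap and on steering at every allocation. The documents claim blinding but not concealed allocation, so there is no concealment claim to withdraw. What is missing is an account of how the next assignment was protected.

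**What to change.** **If women are still being enrolled.** Keep this author as screener and baseline assessor and move the assignment step to another existing author with no role in screening. That author holds the three stratum lists. Each allocation is released, for example by sequentially numbered, opaque, sealed envelopes, only after consent, eligibility, BFI score and stratum are recorded. State a rounding rule for scores between strata.

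Do not disclose block sizes to the screener. If sizes vary, they must fill 24 per stratum: three blocks of 4 and two of 6 in random order do so (3 × 4 + 2 × 6 = 24). Separating the roles is the main protection. Varying sizes helps only if they stay hidden, since a known block of 4 is slightly more guessable than one of 6: [2 + (16/6 − 1)/2]/4 = 70.8%.

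**If enrolment is complete**, as the past tense and final counts suggest:

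- state who held the list, and whether the screener could see it or past assignments;
- report baseline BFI by arm for all 89 randomised women (47 and 42);
- adjust the group comparison for baseline BFI, which Data analysis does not now specify;
- state the lack of described concealment as a limitation.

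**Cost.** The first route needs some preparation and brings a short delay before assignment. It needs no new staff if another author is free of screening, which the documents do not confirm. The second route needs reporting and one adjusted analysis.
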